### 17.3. Power calculation and sample size

Primary outcome: within-individual change in relative abundance of SCFA producers. The study is powered to detect a difference in SCFA producer levels that is equal to or greater than the observed difference in SCFA producer levels from our prospective cohort (6.6% for high vs 3.7% low dietary fiber). The rationale for this is that inulin must be at least as impactful as mixed dietary fiber to be a viable therapeutic. The proposed sample size of 30:30:30 will yield 80% power to detect a minimum difference of 0.73 standard deviations (SD) comparing any one inulin arm to the placebo arm using a two-sided t-test with 0.05 significance level and assuming equal variance. If the inulin arms have similar changes in SCFA producer levels, they will be combined and the study would have 80% power to detect a minimum 0.63 SD for inulin compared to placebo at the .05 significance level. This sample size will also have 80% power to detect 0.33 SD differences among the 3 means versus the alternative of equal means using an F-test at the .05 significance level.

Secondary outcome: MDRO colonization. Power calculations were performed using the observed 42% rate of MDRO colonization in our prospective ICU cohort and 1:1:1 allocation to the intervention. Because this is an early phase study conducted with the expectation that promising results will be followed up by definitive larger studies, sample size calculations are based on one-sided testing with alpha .10 using a t-test based on the binomial distribution. Under these assumptions, a sample size of 90 patients will yield 80% power to detect a 20.4% or less rate of MDRO colonization on Day 7 with inulin, assuming that the two inulin arms are combined. If the inulin arms are not combined, there will be 80% power for a 17.3% or less rate of Day 7 MDRO colonization comparing any one inulin intervention arm vs placebo. The two-sided 95% confidence interval for the effect size estimate within the combined inulin arms would be 7.1 to 26.6% for an estimate centered on 15% and 10.8 to 32.3% for an estimate centered on 20%.

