## 10. Outcomes

Primary and secondary outcomes focus on the comparison of baseline to Day 3 samples. This project will also gather samples at ICU Days 7, 14, and 30. These additional samples will be used to construct longitudinal time series data and test for differences between groups that may be slower to emerge (e.g., baseline vs Day 7 comparisons).

10.1. Primary outcome: Relative abundance of SCFA producers through ICU Day 3. The within-individual change in the relative abundance of SCFA producers will be determined by 16S rRNA gene sequencing of rectal swabs and compared between intervention groups. From extracted rectal swab DNA, polymerase chain reaction (PCR) will be performed on a Bio-Rad T100 Thermal Cycler (Bio-Rad, Hercules, CA) to amplify the V4 hypervariable region of the 16S ribosomal RNA gene with primers derived from Klindworth *et al.* appended with overhang sequences for compatibility with Illumina index and sequencing adapters (Illumina, San Diego, CA). The relative abundance of SCFA producers levels will be determined as the sum total across the bacterial species known to ferment the SCFA butyrate and subtracted within each individual to obtain the change (Day 3 minus baseline).

10.2. Secondary outcome: MDRO colonization status on ICU Day 3. MDRO colonization status will be based on Day 3 rectal swab cultures, classified categorically and compared between intervention groups. MDROs will be defined as methicillin-resistant *Staphylococcus aureus* (MRSA), vancomycin-resistant *Enterococcus* (VRE), and MDR Gram negative bacteria (defined as Gram negatives with *in vitro* non-susceptibility for third-generation cephalosporins). Based on culture results, Day 3 MDRO colonization status will be classified categorically and compared between groups.

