## 17. Statistical methods

### 17.1. Overall plan for statistical analysis

After enrollment is complete, the REDCap dataset will undergo DCC cross-checks for quality and accuracy. The PI will review blinded data to identify errors which, if they exist, will be rectified by reference to paper CRFs or to the EMR. After quality checks are complete, the REDCap dataset will be closed and locked. The biostatistician will then perform an intent-to-treat analysis to determine the primary and secondary outcomes. The DSMO will have complete access both to the raw data and to the analytic code used by the biostatistician and will nominate a qualified monitor who will review this work for rigor. Once this is complete, the primary and secondary outcomes will be finalized. At this point, the locked data will be made available to the PI and other investigators for additional analyses. For all analyses,  $\alpha < 0.05$  will be considered statistically significant and two-sided testing will be performed. When death is a competing risk, Fine and Gray regression analyses will be performed.

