### 17.2. Determination of the primary and secondary outcomes

Primary outcome: within-individual change in relative abundance of SCFA producers. 16S rRNA gene sequencing data will be processed using the QIIME platform with appropriate rarification and filtering. The primary analysis will be intent-to-treat, restricted to the subjects who complete the Day 3 assessment and contribute data. Within-individual change in SCFA producers will be calculated as Day 3 minus baseline relative abundance and an ANOVA or Kruskal-Wallis (KW) test (if skewed data) will be used to assess for differences across the three groups. If there is no significant difference between the low- and high-dose inulin arms, these arms will be combined for comparison against placebo in the final analysis using a two-sample t-test or rank-sum test. Although the primary analysis will be with the Day 3 samples, unadjusted and adjusted longitudinal data analysis will be performed using the generalized estimating equation approach with working independence correlation structure.

Secondary outcome: MDRO colonization. Subjects who culture positive from rectal swabs from Day 3 for MRSA, VRE, or a Gram negative with non-susceptibility to a third generation cephalosporin will be classified as MDRO colonized and all other subjects as not MDRO colonized. The proportion of patients who are MDRO colonized on Day 3 will be compared between intervention groups using a chi-squared test or Fisher's test. For this analysis, patients in the inulin arms will be combined if testing shows no significant difference between these inulin arms. Because baseline colonization status is likely to be an important predictor of Day 3 colonization status, we will test whether baseline MDRO colonization rates differ between intervention groups. If such a difference is observed, we will reanalyze Day 3 MDRO colonization with stratification according to baseline MDRO colonization (baseline MDRO colonized vs not colonized). Exploratory analyses will examine Day 7 MDRO colonization status and semi-quantitative culture data using ANOVA or Kruskal-Wallis testing. The difference in rates of Day 3 MDRO colonization will be taken as the effect size estimate for future trials.

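### The 80% power for MDRO colonization rests on a one-sided 0.10 test at Day 7; the planned Day 3 test, two-sided at 0.05, has 46–58% power at the same rates

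*Combined protocol and SAP*

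**What the plan says.** - **Basis of the power statement (17.3).** For MDRO colonization, "sample size calculations are based on one-sided testing with alpha .10 using a t-test based on the binomial distribution". The reason given is that this is an early-phase study to be followed by larger ones. The placebo rate is 42%, from the investigators' own ICU cohort.
- **Power claimed (17.3).** With the inulin arms combined, "80% power to detect a 20.4% or less rate of MDRO colonization on Day 7 with inulin". With one inulin arm against placebo, "there will be 80% power for a 17.3% or less rate of Day 7 MDRO colonization".
- **Significance rule (17.1).** For all analyses the threshold is 0.05; that level "will be considered statistically significant and two-sided testing will be performed". No exception is made for the secondary outcome.
- **Planned test (17.2).** "The proportion of patients who are MDRO colonized on Day 3 will be compared between intervention groups using a chi-squared test", with Fisher's test as the alternative and no rule for choosing between them.
- **Time point.** Section 10.2 is headed "Secondary outcome: MDRO colonization status on ICU Day 3", and the synopsis agrees. Section 17.2 adds: "Exploratory analyses will examine Day 7 MDRO colonization status".
- **Precision (17.3).** "The two-sided 95% confidence interval for the effect size estimate within the combined inulin arms would be 7.1 to 26.6"% for an estimate of 15%, and 10.8 to 32.3% for 20%. Section 17.2 instead defines the effect size for future trials as the difference in Day 3 rates.

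**The concern.** A power figure is useful only if it belongs to the test that will be run. Here the sidedness, the significance level and the day all differ between the power statement and the analysis plan. Within 17.3 the primary outcome is powered two-sided at 0.05, in line with 17.1, so only the secondary outcome departs.

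Two things are at stake. A null Day 3 result would be read against a claimed 80% power that the planned test does not have. And because 17.3 offers a one-sided 0.10 basis that 17.1 rules out, a reader could argue after the fact for whichever threshold suits the result. The Day 3 difference is also meant to size later trials, yet the plan does not say how precisely it will be estimated.

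**Working it through.** **Inputs.** Placebo rate p₁ = 0.42; inulin rate p₂ = 0.204 (combined) or 0.173 (one arm), all from 17.3. Group sizes are 30 v 60 and 30 v 30, from the 30:30:30 Day 3 completers in 11.1. Losses before Day 3 are replaced, so n is not reduced.

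**Formula (pooled variance, no continuity correction).** Power = Φ[(|p₁ − p₂| − z·s₀)/s₁], where s₀ = √[p̄(1 − p̄)(1/n₁ + 1/n₂)], s₁ = √[p₁(1 − p₁)/n₁ + p₂(1 − p₂)/n₂], and p̄ is the pooled rate.

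- Combined: p̄ = (30 × 0.42 + 60 × 0.204)/90 = 0.276; s₀ = 0.1000; s₁ = 0.1040; difference 0.216.
- One arm: p̄ = (0.42 + 0.173)/2 = 0.2965; s₀ = 0.1179; s₁ = 0.1135; difference 0.247.

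**Step 1: the plan's own figure (one-sided 0.10, z = 1.2816).**
- Combined: (0.216 − 1.2816 × 0.1000)/0.1040 = 0.845, power 80.1%.
- One arm: (0.247 − 1.2816 × 0.1179)/0.1135 = 0.844, power 80.1%.
- Solving for 80% power returns rates of 20.4% and 17.3%. The plan's method is identified and its arithmetic is correct.

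**Step 2: the planned significance rule (two-sided 0.05, z = 1.9600).**
- Combined: (0.216 − 1.9600 × 0.1000)/0.1040 = 0.193, power 57.7%.
- One arm: (0.247 − 1.9600 × 0.1179)/0.1135 = 0.140, power 55.6%.

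**Step 3: exact binomial enumeration of the two tests named in 17.2.**

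| Comparison | Rule | Chi-squared | Fisher |
|---|---|---|---|
| 30 v 60, 42% v 20.4% | one-sided 0.10 | 80.7% | 72.7% |
| 30 v 60, 42% v 20.4% | two-sided 0.05 | 57.7% | 52.2% |
| 30 v 30, 42% v 17.3% | one-sided 0.10 | 81.3% | 72.0% |
| 30 v 30, 42% v 17.3% | two-sided 0.05 | 56.1% | 45.8% |

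With chi-squared, the share of trials significant on the 17.3 basis but not under 17.1 is 80.7 − 57.7 = 23 points (combined) and 81.3 − 56.1 = 25 points (one arm).

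**Step 4: inulin rate detectable with 80% power, two-sided 0.05.**

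| Comparison | Pooled formula | Exact chi-squared | Fisher |
|---|---|---|---|
| Combined | 14.8% | 15.1% | 13.8% |
| One arm | 10.7% | 11.2% | 8.9% |

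For scale only: keeping the stated rates with 80% power at two-sided 0.05 would take 52 placebo patients at 1:2 (3 × 52 = 156 in all) or 53 per arm (3 × 53 = 159), against 90.

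**Step 5: the quoted intervals.** The exact (Clopper-Pearson) limits for 9/60 are 7.1–26.6% and for 12/60 are 10.8–32.3%. They match 17.3, so they are intervals for one proportion in 60 inulin patients. For the difference from a 42% placebo rate (Wald):
- Inulin 15%: SE = √(0.42 × 0.58/30 + 0.15 × 0.85/60) = 0.101; 0.27 ± 1.96 × 0.101, or 7 to 47 points.
- Inulin 20%: SE = √(0.42 × 0.58/30 + 0.20 × 0.80/60) = 0.104; 0.22 ± 1.96 × 0.104, or 2 to 42 points.

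**The case against.** The one-sided 0.10 basis is stated openly and given a reason, so nobody is misled about where the 80% comes from. Section 17.3 speaks only of sample size calculations, so strictly the plan has one decision rule, the one in 17.1. That reading is fair, and it narrows the point: the stated power does not describe the planned test. It does not remove it.

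Fisher's test widens the range. At the stated rates the smallest expected cell count is about 8.3 (30 × 0.276) or 8.9 (30 × 0.2965). Under the common convention of using Fisher only when an expected count is below 5, it would rarely apply and power would be about 56–58%. But the plan names Fisher without a selection rule, so 46% and 52% cannot be excluded.

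The day does not enter the formula, and the cohort cultured for several MDROs was swabbed at admission and 72 hours only (6.1), so Day 7 looks like a drafting slip. If Day 7 were meant, 90 evaluable patients would not be assured, because replacement covers only failure to start treatment or to complete Day 3. The interval point is one of labelling plus a missing figure; the limits themselves are correct.

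**Conclusion.** The concern holds. It is an inconsistency between sections, not a slip in calculation. Under the analysis the plan specifies, power at the stated rates is 58% (chi-squared) or 52% (Fisher) with arms combined, and 56% or 46% for one arm, instead of 80%.

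These figures assume that the 42% placebo rate and the stated inulin rates apply on Day 3; 17.3 gives no time point for the 42%. They also assume 30 evaluable patients per arm. The expected 95% interval for the difference is about ±20 points, which the plan should show because that difference is to size later trials. The primary outcome and the 30:30:30 target are not affected. This should be fixed before unblinding.

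**What to change.** 1. **Align the test and its power**, by one of two routes:
   - in 17.3, restate power and detectable rates for Day 3 under two-sided 0.05 (about 15% combined and 11% one arm by chi-squared); or
   - in 17.1 and 17.2, write an explicit exception that MDRO colonization is tested one-sided at 0.10.
2. **Name the test**, or give a rule for choosing between chi-squared and Fisher. Under the one-sided 0.10 route, Fisher used throughout gives only 73% and 72%.
3. **Change Day 7 to Day 3** in both power sentences of 17.3, and state the time point to which the 42% refers.
4. **Relabel** 7.1–26.6% and 10.8–32.3% as intervals for the colonization rate in the combined inulin arms, and add the expected interval for the between-group difference.

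The cost is wording only, with no extra patients or data. Unless the one-sided exception is adopted, the stated power or the detectable rates become less favourable.

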### 6.1 Evidence supporting the importance of SCFA producers in the ICU

We have assembled two large prospective cohorts now totaling over 500 ICU patients who have contributed rectal swabs and other data. Results from these cohorts confirm the importance of SCFA producers in protecting against pathogen colonization and infection in the ICU.

- **Cohort #1.** A single rectal swab was performed on medical ICU admission for consecutive patients. Swabs were cultured for VRE and residual DNA was extracted for 16S rRNA gene sequencing; patients were then followed for up to 30 days for death or culture-proven infections. In 9 months, **301 patients** were enrolled of whom 91 (30%) were VRE colonized. Thirty-day mortality was 25% and an overlapping 21% patients developed culture-proven MDR infections.

Cohort #1 demonstrated that the bacteria causing infections in the ICU are present as gut colonizers at the time of admission. We tested whether colonizing MDROs predicted subsequent death or culture-proven infection. Presence of the colonizing organism at ICU admission was almost always associated with subsequent organism-specific infection, even after adjusting for

acute severity illness as captured by the Simplified Acute Physiology Score-3 (SAPS-3) and other relevant clinical variables. This was true for VRE (aHR 5.85, 95% CI 2.25-15.2, 16 infections), *C. difficile* (aHR 19.0, 95% CI 4.40-81.8, 9 infections), *Pseudomonas* (aHR 2.37, 95% CI 1.04-5.43, 28 infections), and *Klebsiella spp.* (aHR 3.81, 95% CI 1.10-13.2, 28 infections). To interrogate the process by which MDRO colonization may lead to infection, we also examined MDRO domination defined as  $\geq 30\%$  16S reads corresponding to a potential pathogen. Because this cohort contained VRE culture data, we were able to test whether patients who had *Enterococcus* domination were in fact colonized by VRE. *Enterococcus* domination (15% of the cohort) and VRE colonization (30%) both predicted *all-cause* infection (**Figure 1**). When 30-day mortality was examined as a stand-alone outcome, VRE colonization/domination predicted 40% increased mortality, after adjusting for SAPS-3 score and other factors.

[figure not shown]

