### 7. Study objectives

[figure not shown]
The short-term goal of the study is to test inulin for the prevention of MDRO colonization and infection in the intensive care unit. The long-term goal of this research is to develop antibiotic-free strategies that prevent or ameliorate ICU-acquired infections.

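### The secondary outcome counts patients already colonized at admission, so preventing new acquisition alone may not reach the powered 20.4%, and a split by baseline status is planned only if the arms differ

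*Combined protocol and SAP*

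**What the plan says.** Section 7 sets the aim: "The short-term goal of the study is to test inulin for the prevention of MDRO colonization and infection in the intensive care unit". Section 10.2 defines the secondary outcome as a status at one time: "MDRO colonization status will be based on Day 3 rectal swab cultures, classified categorically and compared between intervention groups". Section 17.2 applies it to everyone with a positive swab: "Subjects who culture positive from rectal swabs from Day 3 for MRSA, VRE, or a Gram negative with non-susceptibility" to a third-generation cephalosporin counts as colonized, whatever the baseline culture showed. Section 11.3 does not exclude patients who are carriers at admission.

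Baseline status enters in one place. Section 17.2 expects it to be an important predictor, tests whether baseline colonization differs between arms, and plans a stratified reanalysis only if it does. The same section carries the Day 3 difference in rates forward as the effect size for future trials.

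Section 17.3 bases power on a control rate obtained "using the observed 42% rate of MDRO colonization in our prospective ICU cohort", and adds that "sample size calculations are based on one-sided testing with alpha .10". With the inulin arms combined, "a sample size of 90 patients will yield 80% power to detect a 20.4% or less rate of MDRO colonization"; for one arm against placebo, "there will be 80% power for a 17.3% or less rate of Day 7 MDRO colonization". Both targets are stated for Day 7, while the outcome is at Day 3.

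On carriage before treatment, Section 6.1 reports for Cohort #1 that 301 patients "were enrolled of whom 91 (30%) were VRE colonized" on a single admission swab. VRE was the only organism cultured in that cohort.

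**The concern.** Carriage on Day 3 is the net of three things: carriers who stay positive, carriers who turn negative, and new acquisitions. Preventing acquisition acts only on the last. If a large share of patients is positive on arrival and stays positive, that share sets a floor under the inulin rate that prevention alone cannot lower. The admission figure for VRE alone in the protocol's own cohort (30%) lies above both powered targets (20.4% and 17.3%).

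Two readings of the result are at stake. A null finding could be taken as failure to prevent colonization when the trial had modest power even for complete prevention. A positive finding could not be attributed to fewer acquisitions or to more losses from the headline comparison. A prevention trial sized on the total-carriage difference would inherit that mixture. Because randomization is expected to balance baseline carriage, the condition that triggers the stratified reanalysis will usually not be met, and no breakdown by baseline status is then planned.

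**Working it through.** **Inputs.** Placebo 42%, targets 20.4% and 17.3%, one-sided alpha 0.10 (Section 17.3); 30 placebo and 60 combined inulin patients (30:30:30, Section 17.3); two-sided 0.05 as the general rule (Section 17.1); admission VRE 91/301 = 30.2%, Wilson 95% CI 25.3% to 35.6% (Section 6.1). The readable text gives no any-MDRO admission rate and no acquisition, loss or persistence rate. Figure 2, which plots colonization at admission and 72 hours by SCFA-producer level, was not available for this check.

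**Formula.** Two proportions, pooled variance under the null, no continuity correction:

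- SE0 = sqrt[p̄(1 − p̄)(1/n1 + 1/n2)]
- SE1 = sqrt[p1(1 − p1)/n1 + p2(1 − p2)/n2]
- power = Φ[(p1 − p2 − z·SE0)/SE1]

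**Step 1: the plan's figures reproduce.**

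- 42% v 20.4%, 30 v 60: p̄ = 0.276, SE0 = 0.1000, SE1 = 0.1041. Power = Φ[(0.216 − 1.2816 × 0.1000)/0.1041] = 80.1%.
- 42% v 17.3%, 30 v 30: 80.1%.

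The arithmetic in 17.3 is right for its inputs.

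**Step 2: turnover needed to reach the targets.** If inulin blocks all acquisition, its rate is the baseline rate b less whatever turns negative. From b = 30%:

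- to 20.4%: (30 − 20.4)/30 = 32% of carriers must turn negative;
- to 17.3%: (30 − 17.3)/30 = 42%.

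For 20.4%, the requirement is 18% from b = 25% and 42% from b = 35%.

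**Step 3: power if acquisition is fully blocked and carriers persist.** With b = 30%: p̄ = 0.34, SE0 = 0.1059, SE1 = 0.1078.

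- One-sided 0.10: Φ[(0.12 − 1.2816 × 0.1059)/0.1078] = Φ(−0.146) = 44%.
- Two-sided 0.05: Φ[(0.12 − 1.96 × 0.1059)/0.1078] = Φ(−0.81) = 21%.

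| Assumed persistent carriage | Power, one-sided 0.10 | Power, two-sided 0.05 |
|---|---|---|
| 20% | 81% | 59% |
| 25% | 64% | 38% |
| 30% | 44% | 21% |
| 35% | 26% | 10% |

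At 30%, reaching 80% power at one-sided 0.10 would take about 107 placebo and 214 inulin patients.

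**Step 4: the sampling time of the 42%.** Steps 2 and 3 treat 42% as the placebo rate at the outcome visit. Section 17.3 does not say when it was observed. If it is an admission rate and carriers persist, complete prevention leaves inulin at 42%, and power depends on the placebo rate at Day 3: 20% power if that is an assumed 47%, 35% at 52%, and 53% at 57% (one-sided 0.10).

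**The case against.** The case against is substantial.

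- **No persistence rate.** Nothing in the documents says how many carriers stay swab-positive. If 32% of a 30% baseline turned negative spontaneously in both arms, blocking acquisition would bring inulin to 20.4% with no clearance by inulin. This stands. It has a cost, though: the same loss would occur on placebo, which would then need 42 − 20.4 = 21.6 points of new acquisition to stay at 42%. The documents give no rate by which to judge that.
- **Unlike figures.** The 30% is VRE only, at admission, in Cohort #1. The 42% is any MDRO and cannot come from that cohort, which cultured VRE alone. This stands: the 44% is a scenario, and subtracting one figure from the other does not estimate acquisition in this trial. Carry-over to septic patients on antibiotics is also assumed. Other MDROs, however, could only add to admission carriage.
- **Day 7.** The power sentences name Day 7, so they do not themselves assume an effect within 72 hours. This stands, but it adds a conflict: the outcome is at Day 3, and neither cohort described in Section 6.1 was swabbed at Day 7.
- **Mechanism.** Sections 5.1 and 6.1 allow for suppression of organisms already present. Section 6.1 also reports a gap of over 25 points in MDRO colonization between high and absent SCFA producers, which is observational but larger than the powered 21.6 points. So total carriage is a legitimate outcome. It still does not isolate prevention.
- **Already handled in part.** The conditional stratification, semi-quantitative cultures and within-patient resistance-gene change all bear on the question. None gives acquisition and loss by arm as a matter of course.
- **Stage.** This is a secondary outcome in an early-phase trial. That limits the weight of the point and supports a remedy by reporting, not redesign.

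**Conclusion.** The point holds in conditional form. The outcome measures total carriage while the goal is prevention, and the planned analysis separates the two only if the arms are found to differ at baseline. If admission carriage is about 30%, all carriers persist and placebo is at 42%, power for complete prevention of acquisition is about 44% at the plan's one-sided 0.10 and 21% at two-sided 0.05, against the stated 80%. Across assumed persistent carriage of 20% to 35%, the one-sided figure runs from 81% to 26%, so at the low end the plan's power is intact.

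A reader might go further in three ways that the documents do not support:

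- That 20.4% cannot be reached by prevention. That needs full persistence and transfer of the Cohort #1 rate, and neither is established.
- That the power statement assumes inulin clears a third of carriers within 72 hours. Loss may be spontaneous, and the sentence refers to Day 7.
- That a positive result would show clearance and not prevention. A randomized difference in total carriage is the net of both.

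**What to change.** In Section 17.2, replace the conditional stratification with unconditional reporting, beside total Day 3 carriage, of two quantities by arm with confidence intervals:

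1. new acquisition among patients negative at baseline;
2. loss of carriage among patients positive at baseline.

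Label both as estimation only.

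In Section 17.3, state that 20.4% and 17.3% are total-carriage rates that preventing acquisition alone may not reach, state when the 42% was sampled, and reconcile Day 7 in the power text with the Day 3 outcome.

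The cost is two tabulations and a few sentences. Baseline and Day 3 swabs for culture are already planned, so no patients, samples or assays are added. The drawback is small subgroups with wide intervals: at 30% baseline carriage, 0.70 × 90 = 63 patients start negative (21 on placebo) and 27 start positive (9 on placebo). The tables would guide interpretation and the sizing of a later trial; they would not support a test.
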